#### Figure 1: Study Flow Diagram

After patients and their legal parents/legal guardians provide informed assent (as appropriate) and informed consent, patients will be assessed for study eligibility.

Patients who have completed their end of study (EOS) visit prior to amendment 4 will be reevaluated for eligibility at a Re-Entry visit for participation in the open-label extension period (Part C) and Safety Follow-up period (see Section 7.2.2.3). Patients who have entered the safety followup period after completing Part B at the time of amendment 4 approval may immediately enter the open-label extension (Part C) without being required to complete an EOS visit prior to entering Part C.

Patients are required to have a documented diagnosis of EoE which may be established either by a prior historical biopsy, as demonstrated by intraepithelial eosinophilic infiltration (peak eosinophils/high power field  $\geq$ 15 eos/hpf) (400×) from at least 1 esophageal region and performed after at least 8 weeks of treatment with an approved PPI regimen, or by biopsies performed after approximately 8 weeks of PPI treatment initiated prior to screening or during the screening period, which demonstrates  $\geq$ 15 eos/hpf) (400×) from at least 2 of the 3 esophageal regions (proximal, mid, and distal); if the PPI regimen is stopped, biopsies must occur within 2 weeks of stopping the PPI. See Figure 2 for endoscopy/biopsy procedure flow chart.

Regeneron Pharmaceuticals, Inc.

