• Part C: Up to 108-Week Open-Label Extension Period: Part C is the open-label extension period of the study. All patients (Part C) will receive higher exposure dupilumab regimens based on body weight at visit 17 (week 52, end of extended active treatment period) or start of open-label period (for re-entry patients). All patients who received lower exposure dupilumab during Part B will be re-assigned to higher exposure dupilumab regimens at the start of the open-label (Part C) period. If weight increases place a patient into a higher weight tier at visit 17 / week 52 (or start of open-label period for re-entry patients) or at specified in-clinic visits in Part C, the patient will be re-assigned to an open-label treatment regimen based on the weight tiered dosing regimen specified below.

Higher exposure dupilumab regimens (Part C):

- mg Q3W in patients who weigh  $\geq$ 5 kg to <15 kg
- mg Q2W in patients who weigh  $\geq 15$  kg to <30 kg
- mg Q2W in patients who weigh  $\geq$ 30 kg to <40 kg
- mg QW in patients who weigh  $\geq$ 40 kg

NOTE: In Part C, only active study drug (dupilumab) will be administered. No matching placebo will be administered in Part C. The weight-based dosing regimens will be as listed above (see Figure 5).

For Part C only: Patients located in a country where dupilumab is commercially available for treatment of EoE in patients  $\geq$ 12 years old will be provided treatment with study drug until they are both (1) at least 12 years of age and (2) weigh at least 40 kg or the lowest weight for which the indication is approved for EoE. These patients will have an end of treatment visit at the next scheduled study visit upon meeting both criteria, followed by an end of study follow-up visit after 12 weeks.

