## Table 4: Schedule of Events Open-Label Extension Part C (OLE) and EOS Schedule of Events

							0	pen-La	abel Ex	tensio	n Perio	d									12-Week Follow- Up
Study Procedure	V 17 	PV 19 	PV 20 	V 21	PV 22 	V 23	PV 24 	V 25	PV 26 	V 27	PV 28 	V 29	PV 30 	V 31	PV 32 	V 33	PV 34 	V 35	PV 36 	EOT V37	EOS  V38
Week (W)	W 52	W 56	W 60	W 64	W 72	W 76	W 84	W 88	W 96	W 100	W 108	W 112	W 120	W 124	W 132	W 136	W 144	W 148	W 152	W 160	Last Visit +12 Wk
Day (D)	D 365	D 393	D 420	D 449	D 505	D 533	D 589	D 617	D 673	D 701	D 757	D 785	D 841	D 869	D 925	D 953	D 1009	D 1037	D 1065	D 1121	Last Dose +84D
Visit Window (Davs [d])	±7d	±7d	±7d	±7d	±7d	±7d	±7d	±7d	±7d	±7d	±7d	±7d	±7d	±7d	±7d	±7d	±7d	±7d	±7d	±7d	+7d
Age in Months	X9	Х	Х	Х	Х	Х	Х	Х	Х	Х	Х	Х	Х	Х	Х	Х	Х	Х	Х	Х	Х
Weight, Height (or length for patients <2 years of age) 	X9			Х		Х		Х		Х		Х		X		Х		Х		Х	Х
EoE- EREFS 										Х										Х	
Endoscopy with biopsies										Х										Х	
Pediatric Eosinophilic Esophagitis Symptom Score: Caregiver version (PEESSv2.0) 	Х					X				X						Х				Х	
Pediatric EoE Impact Scale: 	X9					Х				Х						Х				Х	

							0	pen-La	abel Ex	tensio	n Perio	od									12-Week Follow- Up
Study Procedure	V 17 	PV 19 	PV 20 	V 21	PV 22 	V 23	PV 24 	V 25	PV 26 	V 27	PV 28 	V 29	PV 30 	V 31	PV 32 	V 33	PV 34 	V 35	PV 36 	EOT V37	EOS  V38
Week (W)	W 52	W 56	W 60	W 64	W 72	W 76	W 84	W 88	W 96	W 100	W 108	W 112	W 120	W 124	W 132	W 136	W 144	W 148	W 152	W 160	Last Visit +12 Wk
Day (D)	D 365	D 393	D 420	D 449	D 505	D 533	D 589	D 617	D 673	D 701	D 757	D 785	D 841	D 869	D 925	D 953	D 1009	D 1037	D 1065	D 1121	Last Dose +84D
Visit Window	±7d	±7d	±7d	±7d	±7d	±7d	±7d	±7d	±7d	±7d	±7d	±7d	±7d	±7d	±7d	±7d	±7d	±7d	±7d	±7d	+7d
(Days [d]) Patient version (PEIS-P) Caregiver version (PEIS-C)																					
Global Impression of Severity:  Patient version (GIS-P) Caregiver version (GIS-C) Clinician version (GIS- Clin)	X9					X				X						X				X	
Safety:		1					1		1		1				1		-				
Vital signs	Х			X		Х		Х		X		X		X		X		X		X	X
examination										Λ										Λ	Λ
Adverse events	Х	Х	Х	Х	Х	Х	Х	Х	Х	Х	Х	Х	Х	Х	Х	Х	Х	Х	Х	Х	Х

Regeneron Pharmaceuticals, Inc.

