- 15. The Pediatric Eosinophilic Esophagitis Symptom Score (PEESS) version 2.0 will be completed by caregivers of patients ≥1 to <12 years of age (determined at the time of screening visit 1).
- 16. Exit interviews will be conducted by a trained interviewer by telephone within 14 days of completing week 16/visit 8. These interviews will be completed with caregivers. Patients aged ≥8 to <12 years old (determined at the time of screening visit 1) may also join a portion of the exit interview.

#### 9.1.1.2. Footnotes for Table 2

- 1. This visit is the same as the week 16 visit for the double-blind study portion (Table 1), and all other assessments indicated for week 16 (Table 1) should be performed. Endoscopy with biopsies at visit 8/week 16 must be completed prior to administration of study drug for Part B Extended Active Treatment.
- 2. Study assessments will be performed, and blood samples will be collected prior to administration of study drug. In the event of suspected SAEs, such as anaphylaxis or hypersensitivity, functional dupilumab PK sample and anti-dupilumab antibody sample may be collected at or near the event.
- 3. In addition to predose assessments, AEs and vital signs (body temperature, blood pressure, respiratory rate, and heart rate) will be assessed at 30 minutes (±10 minutes) post-dose.
- 4. 4a. Study drug administration will continue through week 50.

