7. Endoscopy/imaging for EoE-EREFS/biopsy procedures should be performed after all other efficacy and safety assessments. Minor esophageal features will be assessed by the investigator.

7a. For patients who receive rescue treatment, endoscopy/EoE-EREFS/biopsy procedures will be performed prior to initiation of rescue treatment. Patients undergoing endoscopy/biopsy prior to rescue will not undergo the scheduled endoscopy/biopsy at weeks 16 and 52.

- 8. In addition to the predose assessments, AEs and vital signs (body temperature, blood pressure, respiratory rate, and heart rate) will be assessed at 30 minutes (±10 minutes) post-dose at visit 8.
- 9. In case of a positive urine pregnancy test, the study treatment will be withheld and a serum pregnancy test to confirm the pregnancy should be performed as soon as possible. A confirmed pregnancy will lead to study drug discontinuation in all cases.
- 10. Urinalysis is only required for patients aged  $\geq 6$  years.
- 11. The Pediatric Eosinophilic Esophagitis Symptom Score (PEESS) version 2.0 will be completed by caregivers of patients >1 to <12 years of age (determined at the time of screening visit 1).
- 12. Assessments indicated for this week 52 (end of extended active treatment) visit should be performed for all patients. For patients who will enter the open-label extension period, there are additional events listed for the week 52 visit in Table 4.
- 13. For a complete list of procedures to be performed for Re-Entry patients, please see Table 4.

#### 9.1.1.3. Footnotes for Table 3

- 1. Patients who are withdrawn from study drug will be asked to complete the 12-week followup period and the end of study visit.
- 2. The PESQ-P will be completed daily by patients ≥8 to <12 years of age (determined at the time of screening visit 1) just before going to bed for the night. The PESQ-C will be completed daily by caregivers of patients ≥1 to <12 years of age (determined at the time of screening visit 1) after the patients go to bed for the night. The PESQ-P and PESQ-C will be completed via an electronic diary (diary) and site personnel should conduct regular checks of patient and caregiver diary compliance. The PEIS-P and PEIS-C will be completed during site visits as indicated in the Schedule of Events table by the patients and caregivers, respectively.

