#### 11.4.5.1. Adverse Events

#### **Definitions**

For safety variables, 2 observation periods are defined:

- The pretreatment period is defined as the time from signing the ICF to before the first dose of study drug.
- The treatment-emergent period is defined as the day from first dose of study drug to end of study. The treatment-emergent period includes the double-blind treatment period, extended active treatment period, and open-label extension period (up to 160 weeks in total) and the 12-week follow-up period.
  - Treatment period: date of the first dose of study drug to week 160 visit date for those patients who completed the week 160 visit with available visit date; or date of the first dose of study drug to study day 1121 (study day 1 being the first dose date) or the date of patient last contact, whichever is earlier, for those patients who did not complete week 160 visit or had missing week 160 visit date
  - Follow-up period: date after the end of treatment period to end of study

Treatment-emergent adverse events are defined as those that are not present at baseline or represent the exacerbation of a pre-existing condition during the treatment-emergent period.

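### The exposure formula adds 14 days whatever the injection interval, and the safety treatment period has no end date for children who by design finish before week 160

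*Protocol*

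**What the plan says.** **Exposure.** Section 11.4.5.3 calculates duration in each part as last injection date minus first injection date, plus a fixed 14 days. Sections 8 and 8.1 set the injection schedules:
- Part A: every two weeks for all.
- Part B: every two weeks below 60 kg and weekly at 60 kg or more.
- Part C: every three weeks below 15 kg, every two weeks from 15 kg to below 40 kg, and weekly at 40 kg or more.

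**Period boundary.** In Section 11.4.5.1 the treatment period ends at the week 160 visit for children with a dated week 160 visit. For all others it ends at "study day 1121 (study day 1 being the first dose date) or the date of patient last contact, whichever is earlier". The next line reads "Follow-up period: date after the end of treatment period to end of study". The treatment-emergent period runs from first dose to end of study and is described as covering the parts up to the "open-label extension period (up to 160 weeks in total) and the 12-week follow-up period".

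**Planned finishes before week 160.**
- Part B: footnote 4a to Table 2 says "Study drug administration will continue through week 50". Footnote 12 says "For patients who will enter the open-label extension period, there are additional events listed for the week 52 visit in Table 4", so not every Part B completer has to go on. Section 6.1 confirms that a follow-up directly after Part B exists: "Patients who have entered the safety followup period after completing Part B at the time of amendment 4 approval may immediately enter" Part C.
- Part C: under Section 8.1, children who reach the age and weight criteria have an "end of treatment visit at the next scheduled study visit upon meeting both criteria", then an end-of-study visit 12 weeks later. Section 6.1 also ends Part C at commercial availability.
- Table 4 times the end-of-study visit as "Last Visit +12 Wk" in its week row, and as 84 days after the last dose in its day row.

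**The concern.** A fixed 14 days represents one injection interval only when injections are two weeks apart. For the other schedules the formula misstates a duration that the protocol plans to report.

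The period boundary depends on whether a child reached week 160, not on whether treatment had ended. For a child whose planned end of treatment comes earlier, the last contact is normally the end-of-study visit. The treatment period then runs through the follow-up. The same 12 weeks count as follow-up for a week 160 completer. A summary by period that used this boundary would place events from off-drug time under treatment.

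**Working it through.** **1. Reproduce the protocol's own figures.** Study day = 7 × week + 1.
- Week 160: 7 × 160 + 1 = 1121, the cap in Section 11.4.5.1.
- A full Part B course injected every two weeks, from week 16 (day 113) to week 50 (day 351): 351 − 113 + 14 = 252 = 36 × 7. The exposure formula is exact for this schedule.

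**2. Exposure formula on other schedules.** Error = 14 − injection interval.

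| Injection schedule | Where | Error | Relative to planned part |
|---|---|---|---|
| Every 2 weeks, including four-weekly dupilumab with alternating placebo | Parts A, B, C | 14 − 14 = 0 | none |
| Weekly | Part B, 60 kg or more | 14 − 7 = +7 days | 7/252 = 2.8% |
| Weekly | Part C, 40 kg or more | 14 − 7 = +7 days | 7/(108 × 7) = 7/756 = 0.9% |
| Every 3 weeks | Part C, below 15 kg | 14 − 21 = −7 days | 7/756 = 0.9% |

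**3. Period boundary, Part B completer who does not continue.** Last dose is day 351 and the week 52 visit is day 365.
- End of study by last dose: 351 + 84 = 435. By last visit: 365 + 84 = 449.
- Both precede day 1121, so the treatment period ends on day 435 or 449 and follow-up is 0 days.
- Days labelled treatment after the week 52 visit: 435 − 365 = 70, or 449 − 365 = 84. The treatment period is 70/365 = 19% to 84/365 = 23% too long.
- Counted from the last dose: 84 to 98 days.

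**4. Period boundary, planned Part C exit without interruption.** End of study = end-of-treatment (EOT) day + 84 (Section 8.1). Treatment-period end = the smaller of 1121 and EOT day + 84.

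| EOT visit | EOT day | End of study | Treatment-period end | Follow-up days labelled treatment |
|---|---|---|---|---|
| V21, week 64 | 449 | 533 | 533 | 84 of 84 |
| V27, week 100 | 701 | 785 | 785 | 84 of 84 |
| V35, week 148 | 1037 | 1121 | 1121 | 84 of 84 |
| Phone visit, week 152 | 1065 | 1149 | 1121 | 56 of 84 |
| V37, week 160 | 1121 | 1205 | 1121 | 0 of 84 |

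The excess is 84/449 = 19% of the treatment period at V21 and falls to 84/1037 = 8% at V35. For EOT between days 1038 and 1120, only 1121 − EOT day of the 84 days are relabelled. V35 fits only at its nominal day: if it is 7 days late (day 1044), the end of study is day 1128 and 1121 − 1044 = 77 of 84 days are relabelled.

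**The case against.** The strongest reply is that no output specified in the protocol depends on the treatment/follow-up split. That stands. The relabelled days lie inside the treatment-emergent period either way, so no event gains or loses treatment-emergent status and the summaries in Section 11.4.5.1 are unchanged. The protocol specifies no table of treatment against follow-up and no exposure-adjusted rate.

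A reader might infer that the part-specific endpoints in Section 4.1.2 are therefore wrong. The documents do not support this: the span in Section 11.4.5.1 sets no boundary between Parts A, B and C, and the statistical analysis plan, which is not at hand, may define those windows.

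A reader might also infer that every early finisher loses the whole follow-up. That fails for exits after V35 and for late visits near the cap, as shown. Nor does the reference to a 12-week follow-up contradict the rule; it describes the full design and does not promise each child a non-empty follow-up.

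A single clock from first dose also fits re-entry children poorly, but the length of their off-study gap is not stated, so no size can be given and none is claimed.

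Could an early end-of-treatment visit be recorded as the week 160 visit, since Table 4 labels V37 as EOT? Section 11.4.5.1 does not say so, and a Part B completer who stops there has no V37.

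On exposure, the reply concerns size only: at most 7 days per part, and in Part B only for children who reach 60 kg after entry, since Section 7.2.2.1 excludes that weight at screening. This is fair, but the formula is still wrong for those schedules.

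**Conclusion.** Both rules are wrong as written, and both are minor.

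The exposure error is certain for the affected schedules: +7 days for weekly injections and −7 days for three-weekly injections, per child and part. It is zero for two-weekly injections.

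The boundary error relabels 70 to 84 days after the week 52 visit for a Part B completer who stops there, and 84 days for a planned in-clinic Part C exit up to V35. It leaves those children no follow-up period. This rests on nominal visit days and on the end-of-study visit being the last contact. For commercial-availability exits it also assumes the same visit sequence, which the protocol spells out only for the age and weight exits. How many children are affected is not given.

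The claim does not extend to children who stop drug early but stay for their scheduled visits (Section 8.4.2); a scheduled-period window is defensible for them.

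**What to change.** - **Section 11.4.5.3:** replace the fixed 14 days by the injection interval of the child's assigned schedule at the last injection, counting placebo injections as now.
- **Section 11.4.5.1, children who complete or leave a study part by design and do not continue:** end the treatment period at that part's end-of-treatment visit and start follow-up the next day.
- **Section 11.4.5.1, all other children without that visit:** end the treatment period at the earlier of the scheduled end of the part and last contact. Children who stop drug but stay in the study then keep the scheduled window.
- **Table 4:** reconcile the two timings of the end-of-study visit, which give days 435 and 449 for the same Part B completer.

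The two analysis changes need wording and derivation code only. No new data are required, and treatment-emergent counts over the whole study stay the same.

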#### Analysis

All AEs will be coded using the Medical Dictionary for Regulatory Activities (MedDRA®).

Summaries of all TEAEs by treatment group will include:

- The number (n) and percentage (%) of patients with at least 1 TEAE by SOC and PT
- TEAEs by severity (according to the grading scale outlined in Section 10.2.4), presented by SOC and PT
- Treatment-related TEAEs, presented by HLT, SOC and PT
- TEAEs leading to permanent treatment discontinuation, presented by SOC and PT
- Treatment-emergent AESIs (defined with a PT or a prespecified grouping)

Serious adverse events leading to death and other SAEs will be summarized by treatment group.

## 11.4.5.2. Other Safety

#### Vital Signs

Vital signs (temperature, pulse, blood pressure, and respiration rate) will be summarized by baseline and change from baseline to each scheduled assessment time with descriptive statistics.

The number and percentage of patients with a treatment-emergent potentially clinically significant value (PCSV) will be summarized for each vital sign variable. The criteria for treatment-emergent PCSV will be defined in the SAP.

## Laboratory Tests

Laboratory test results will be summarized by baseline and change from baseline to each scheduled assessment time with descriptive statistics.

Number and percentage of patients with a treatment-emergent PCSV will be summarized for each clinical laboratory test. The criteria for treatment-emergent PCSVs will be defined in the SAP.

Shift tables based on baseline normal/abnormal and other tabular and graphical methods may be used to present the results for laboratory tests of interest.

## 11.4.5.3. Treatment Exposure

The duration of exposure during part A, part B and part C of the study will be presented by treatment group and calculated as:

(Date of last study drug injection in the specific study part – date of first study drug injection in the specific study part) + 14 days

Number (%) of patients exposed to study drug during each study part and cumulatively across study parts will be presented by specific time periods for each treatment group. The time periods of interest will be specified in the SAP.

In addition, duration of exposure during the study will be summarized for each treatment group using number of patients, means, standard deviation, minimums, medians, and maximums.

A summary of the number of doses by treatment group will be provided.

## 11.4.5.4. Treatment Compliance

The compliance with study treatment will be calculated for each study part as follows:

Treatment Compliance = (Number of study drug injections during exposure period)/(Number of planned study drug injections during exposure period)  $\times 100\%$ 

The treatment compliance will be presented by specific ranges for each treatment group. The ranges of interest will be specified in the SAP.

## 11.4.6. Pharmacokinetics

## 11.4.6.1. Analysis of Drug Concentration Data

The concentrations of functional dupilumab in serum will be summarized by descriptive statistics at each time point. No formal statistical hypothesis testing will be performed.

## 11.4.7. Analysis of Immunogenicity Data

Immunogenicity will be characterized by the ADA and NAb response observed:

Regeneron Pharmaceuticals, Inc.

CONFIDENTIAL

- Pre-existing immunoreactivity, defined as a positive ADA assay response at baseline, with all post-dose ADA results negative, or a positive assay response at baseline, with all post-dose ADA assay responses less than 4-fold over baseline titer levels
- Treatment-emergent ADA response, defined as any post-dose positive ADA assay response when the baseline results are negative or missing
- Treatment-boosted ADA response, defined as any post-dose positive ADA assay response that is 4-fold over baseline titer levels when baseline is positive in the ADA assay
- Maximum ADA titer values
  - Low (titer <1,000)
  - Moderate  $(1,000 \le \text{titer} \le 10,000)$
  - High (titer >10,000)
- NAb status for samples that are positive in the ADA assay

Incidence of treatment-emergent ADA and NAb will be assessed as absolute occurrence (N) and percent of patients (%), grouped by dose group and ADA titer level.

Plots of drug concentrations will be examined and the influence of ADAs and NAbs on individual PK profiles evaluated. Assessment of impact of ADA and NAbs on safety and efficacy may be provided.

## 11.4.8. Analysis of Pharmacodynamic and Exploratory Biomarker Data

Biomarker results will be summarized by baseline, measured values, change from baseline, and percent change from baseline to each scheduled assessment time point with descriptive statistics. Exploratory analyses performed on biopsies will not be reported in the CSR. Other exploratory analyses may be performed but will not be described in the SAP or CSR.

## **11.4.9.** Timing of Statistical Analysis

The primary analysis may be performed when the last patient completes 16 weeks of treatment duration in Part A. No changes in the conduct of the study will be made based on this primary analysis. The assessment of primary and secondary endpoints specified in Section 4.1.1 and Section 4.1.2 will be analyzed descriptively in Part B as the final analysis. Part C will be described descriptively. Hence, there will be no need for alpha adjustment due to the primary analysis.

In order to maintain study integrity (with respect to the extended active treatment and posttreatment follow-up safety visits) in the event a decision is made to perform the primary analysis, a dissemination plan will be written. This plan will clearly identify the team (including the statistician) that will perform the primary analysis and all related activities, restrict other clinical team members and other sponsor personnel from access to individual patient treatment allocation and site level analysis results, and ensure that the dedicated team will not participate in the data review or data decisions for the following extended active treatment safety analyses.

